9.2 Primary Endpoint

9.2.1 Primary Endpoint Analysis

The primary endpoint, the time from randomization to the first adjudicated occurrence of the composite MACE endpoint in the two treatment groups, will be analyzed using the Kaplan-Meier estimator of the survival function and the log-rank test, stratified for age (<75 and ≥75 years of age) and region and based on the FAS.

Pseudo SAS code for Kaplan-Meier/log-rank test:

```
PROC LIFETEST DATA=<DATA> PLOTS=SURVIVAL();

TIME AVAL*CNSR(1);

STRATA <STRAT1 STRAT2> /GROUP=ARMN TEST=LOGRANK;
RUN;
```

The hazard ratio, comparing the hazard rate of the distribution of the time from randomization to the MACE composite endpoint between the degarelix and leuprolide arms, will be estimated based on the stratified Cox regression model, stratified by age-group and region and including treatment as a factor. The variance estimate of the log hazard ratio will be obtained from the inverse of the observed information matrix for the partial likelihood. An approximate 95% CI for the hazard ratio will be calculated by exponentiation of the 95% CI for the log hazard ratio. Although, the score test for this stratified Cox Regression model is equivalent to the stratified log-rank test, (Kalbfleisch and Prentice, 2002), the (Wald based) 95% CI may not be fully consistent with the stratfied log-rank test. The latter, however, defines the success of the trial. More precisely, the trial will be declared positive if a statistically significant (at two-sided 5% significance level) reduction in the hazard rate of the time from randomization to the composite MACE endpoint is demonstrated in the FAS based on the stratified log-rank test, for patients randomized to degarelix compared to leuprolide.

TLF Figure: Primary Endpoint: Time to First Adjudicated MACE – FAS

Page 25 of 51

9.2.2 Sensitivity Analyses

9.2.2.1 Sensitivity Analysis: Time from randomization to the first confirmed (adjudicated) occurrence of non-fatal myocardial infarction, non-fatal stroke, non-fatal unstable angina requiring hospitalization, or all-cause death

Time from randomization to the first confirmed (adjudicated) occurrence of non-fatal myocardial infarction, non-fatal stroke, non-fatal unstable angina requiring hospitalization, or all-cause death is defined similarly as the primary endpoint with the addition of cardiovascular events unstable angina requiring hospitalization. Also, the endpoint will be analyzed as for the primary endpoint.

9.2.2.2 Sensitivity Analysis: Time to first confirmed occurrence of a MACE related adverse event (MI SMQ (broad); Central nervous system hemorrhages and cerebrovascular conditions SMQ (broad); all-cause death)

Time to first confirmed occurrence of a MACE related adverse event is defined as for the primary endpoint with events being; any adverse event within the broad SMQ term 'myocardial infarction', any adverse event within broad SMQ term 'Central nervous system hemorrhages and cerebrovascular conditions' or all-cause death. Also, the endpoint will be analyzed as for the primary endpoint.

9.2.2.3 Sensitivity Analysis: Total occurrence of (adjudicated) myocardial infarction, stroke, and all-cause death

Total occurrence of myocardial infarction (MI), stroke and all-cause death is defined as the total number of events (MI, stroke or death) occurring over the duration of the trial.

The endpoint will be compared between treatment groups using a negative binomial model. The estimated treatment difference with a 95% confidence interval will be presented.

9.2.2.4 Sensitivity Analysis pertaining to treatment discontinuation or initiation of prohibited therapies related to hormonal therapy

For the purposes of this sensitivity analysis, patients will NOT be censored at the time of treatment discontinuation or initiation of prohibited therapies related to hormonal therapy. Rather, information pertaining to all observed occurrences of the first adjudicated MACE event in patients randomized in the study will be used. Patients will be censored at lost to follow-up/withdrawal from study or day 336, whichever occurs first.

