### Definition of Terms

Investigator	A Medical Doctor at the trial center responsible for the conduct of the clinical trial.
Sponsor	Ferring Pharmaceuticals A/S, Copenhagen, Denmark
Month	One treatment month is equal to 28 days/4 weeks
Trial-related Activity	Any procedure that would not have been performed during the normal management of the patient
Screened	Patient who has signed informed consent
Randomization	Patient is randomly assigned to a treatment group and given a unique patient number

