##### 3.1.2 Overall Design and Control Methods

###### Trial Design

This is a multi-center, randomized, assessor-blind, controlled trial to compare the occurrence of MACEs in patients with prostate cancer and concurrent CVD receiving either monthly treatment with degarelix or leuprolide 3-month depot for 1 year. Patients will be screened within 21 days prior to randomization for compliance with the inclusion and exclusion criteria. A trial design diagram is provided in [Figure 1](#).

Patients will be randomized to one of the two treatments in a 1:1 ratio stratified by baseline age group and region, as detailed in Section 4.2.2. After randomization, the management of prostate cancer is intended to reflect standard-of-care. Monitoring for possible MACEs will occur throughout the trial applying a specific Clinical Events Classification (CEC) process ensuring blinding of the assessors as described in Section 7.1.1.

Patients should be evaluated by a CV specialist to ensure that their CVD treatment is according to standard-of-care before trial entry. Cardiovascular disease information and source medical documents will be requested by the Investigator from the patient's CV specialist to evaluate and document CVD history for eligibility, using a Medical / CV History Request Form. A process will be implemented for the collection and review of supporting source data (with the involvement of the contract research organization [CRO] and Duke Clinical Research Institute [DCRI]) to ensure

the accuracy of patients' medical records documentation for the CVD-related inclusion criteria. The Investigator should ensure that pre-existing CVD and any CVD that may be diagnosed during the trial is managed by a CV specialist according to standard clinical practice. After randomization, the management of CVD and prostate cancer is intended to reflect standard-of-care.

If a patient experiences a CV event during the course of the trial, the Investigator will be encouraged to let the patient continue in the trial if this is not considered to constitute a safety concern. Patients who prematurely withdraw from the trial or from treatment with investigational medicinal product (IMP) will be followed-up for potential CV events and hospitalizations throughout the trial period as described in Section 4.4. If a patient is lost to follow-up, all attempts have to be made to obtain the vital and medical status of the patient at the planned end-of-trial for the patient.

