A patient who prematurely discontinues treatment with IMP, or receives prohibited medication (Section 4.3.2), should be called in for an end-of-treatment visit (Section 6.5) as soon as possible (within 30 days) after a decision of treatment discontinuation has been taken. The reason for premature IMP discontinuation should be recorded in the eCRF. The patient should then be contacted by telephone each month throughout the trial period for collection of follow-up information on hospitalizations and potential CV events, and concomitant medication. At the telephone follow-ups, information will be collected using the standardized questions regarding hospitalizations and/or ER visits that may have occurred since the last telephone follow-up as described in Section 8.2.3. In case the patient has experienced a potential CV event, related event documentation will need to be collected for evaluation by the CEC Committee. After 336 days of participation in the trial, the patient should be called in for an end-of-trial visit (Section 6.6).

In case a patient is lost to follow-up, despite every attempt (e.g., certified mail, telephone contact of patient or patient relatives) to get in contact, the vital and medical status of the patient should be investigated an additional last time at the end of the trial for that patient (i.e. 12 months after Visit 1), by accessing the patient's hospital records, or publicly available sources such as national registries, newspaper obituaries and social networking websites. Attempts may also be made to contact the patient or his relatives to ascertain this information. However, the patients have the right to withdraw their consent for collection of this information at any time, without the need to justify their decision.a

In case the patient has withdrawn his consent for participation in the trial, including any follow-up activities, no new data can be entered into the eCRF and data are recorded in the medical records only. Correction of previous data entries and/or entering of data related to visits/procedures done prior to but made available after withdrawal of consent (e.g. laboratory results) will be allowed unless the patient disapproves it.

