### **14.5 Patient Information and Consent**

The Investigator (or a medically qualified person delegated by the Investigator) will obtain a freely given written consent from each patient after an appropriate explanation of the aims, methods, anticipated benefits, potential hazards, and any other aspects of the trial which are relevant to the patient's decision to participate. The trial patient must be given ample time to consider participation in the trial, before the consent is obtained. The Informed Consent Documents must be signed and dated by the patient and the Investigator who has provided information to the patient regarding the trial before the patient is exposed to any trial-related procedure, including screening tests for eligibility.

The Investigator (or the person delegated by the Investigator) will explain that the patient is completely free to refuse to enter the trial or to withdraw from it at any time, without any consequences for his further care and without the need to justify his decision.

Each patient will be asked to permit the Investigator to obtain CVD information and source medical documents from the patient's CV specialist to evaluate and document CVD history for eligibility. Each patient will also be asked to permit the Investigator to obtain medical documentation from other hospitals or medical centers regarding ER treatment or CV events for the patient during the trial period. In addition, each patient will be asked to permit the Investigator to obtain health-related follow-up information, e.g. by contacting the patient or his relatives, or access hospital records or publicly available sources such as national registries, newspaper obituaries and social networking websites, for a period of not more than 12 months after the patient has entered the trial.c

The patient will receive a copy of the Patient Information and his signed Informed Consent Form covering participation in the trial.

If new information becomes available that may be relevant to the trial patient's willingness to continue participation in the trial, a new Patient Information and Informed Consent Form will be forwarded to the IRBs/REBs/IECs (and regulatory authorities, if required). The trial patients will be informed about this new information and re-consent will be obtained.

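### Deaths found by the protocol's end-of-trial trace of lost patients have no stated route into any time-to-event analysis, because the SAP censors at loss to follow-up

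*SAP*

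**What the plan says.** **The trace.** Protocol 3.1.2 says that for a lost patient "all attempts have to be made to obtain the vital and medical status of the patient at the planned end-of-trial for the patient". Protocol 4.4 names the sources (hospital records, public sources such as registries and obituaries, relatives) and says that status should be "investigated an additional last time at the end of the trial for that patient (i.e. 12 months after Visit 1"). Protocol 8.4.1 refers back to this procedure.

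**Other early leavers.** A separate rule in 3.1.2 covers withdrawals: "Patients who prematurely withdraw from the trial or from treatment with investigational medicinal product (IMP) will be followed-up for potential CV events", as set out in 4.4. Section 4.4 bars new eCRF data once a patient has withdrawn consent for all follow-up.

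**The censoring.** SAP 9.1 sets a default for time-to-event endpoints: censor at the earliest of treatment discontinuation, prohibited hormonal therapy, loss or withdrawal, and Day 336. SAP 9.2.2.4 drops the first two and keeps the rest: "Patients will be censored at lost to follow-up/withdrawal from study or day 336, whichever occurs first". The same section says that it uses every observed first adjudicated MACE in randomized patients. SAP 9.3.4 (all-cause death) has no censoring rule of its own. Protocol 9.6.1 and 9.6.2 carry the same default and the same sensitivity analysis.

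**Months.** The protocol's Definition of Terms states: "One treatment month is equal to 28 days/4 weeks". Table 1 counts Day 336 from Visit 2.

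**The concern.** All-cause death is a component of MACE and an endpoint in its own right. It is also the outcome that a search of registries and obituaries can establish even when the patient cannot be reached. The protocol asks sites to make that search and asks patients at entry to consent to it. The SAP then ends each lost patient's follow-up before the date on which the search could add anything.

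At stake is the analysis that comes closest to following everyone to Day 336. If loss is related to death, censoring at loss biases it, and the data that could show this would have been collected and left unused. The wording also pulls two ways. One programmer could follow the sentence on using all observed events and another the sentence on censoring at loss, and they would report different event counts.

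**Working it through.** **1. Where could a traced death before Day 336 enter?**

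- Primary analysis (SAP 9.2.1): no. The default in 9.1 censors at loss, or earlier at treatment discontinuation.
- Sensitivity analyses 9.2.2.1 and 9.2.2.2: no. They are analyzed as the primary endpoint.
- 9.2.2.4: no on its censoring sentence; yes on its sentence about observed events. The two conflict.
- All-cause death (9.3.4), CV death (9.3.5) and the other CV endpoints (9.3.1 to 9.3.3): no. The default applies.
- PFS (9.3.6): no. It censors at discontinuation or withdrawal, and the default covers loss.
- 9.2.2.3: possibly. It is a negative binomial count over the trial and states no censoring at loss.

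Neither document defines the date of loss or says whether a patient found by the trace still counts as lost.

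**2. The plan's own figures.** With the SAP's hazards of 0.0523 and 0.1076 per year (ratio 0.486), Schoenfeld's formula gives 4 × (1.960 + 0.842)² / (ln 0.486)² = 60.3, so 61 events, as in SAP 3.2.1. With one year of follow-up and a competing 5% annual drop-out, the mean event probability is 0.0746. Then 61/0.0746 = 818 patients (stated: 811) and 66/0.0746 = 885 (stated: 876), both within about 1%. The 5% drop-out is therefore used below as the planning rate of loss.

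**3. Expected MACEs between loss and Day 336.** Inputs: drop-out hazard d = −ln(0.95) = 0.0513 per year; T = 336/365.25 = 0.920 years; event hazard λ. The hazard after loss is kλ, with k assumed, since the documents give no value.

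- Lost before an event: N × d/(d + λ) × [1 − exp(−(d + λ)T)]
- MACEs after loss: N × ∫₀ᵀ d·exp(−(d + λ)t) × [1 − exp(−kλ(T − t))] dt

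For the trial as it ended (SAP section 3: 545 randomized, 14 with events), taking full 336-day exposure, λ = −ln(1 − 14/545)/0.920 = 0.0283 per year. For the planned 876 patients, the SAP's two hazards are used with 438 per arm.

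| N | Lost | k = 1 | k = 2 | k = 3 | k = 5 |
|---|---|---|---|---|---|
| 545 | 24.8 | 0.32 | 0.64 | 0.95 | 1.56 |
| 876 | 38.9 | 1.42 | 2.76 | 4.03 | 6.38 |

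Hand check for 545 at k = 1: 24.8 lost × about 0.46 years remaining on average × 0.0283 = 0.32.

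These are MACEs of all kinds, so they are upper limits for traced deaths. One event is 1/14 = 7% of the total, and 1.56 is 11%. Power hardly moves: at HR 0.49 without the futility look, 66 events give 82.6% and 67 give 83.1%.

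**4. The date of the trace.** Visit 1 is up to 21 days before Visit 2.

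- With 28-day months, 12 × 28 = 336 days from Visit 1 falls between Day 315 and Day 336 from Visit 2. Up to 21 days, or 21/336 = 6.25% of follow-up, lie beyond the trace. At N = 876 that is 0.17 (k = 1) to 0.71 (k = 5) expected MACEs among lost patients.
- With calendar months, 365 days from Visit 1 is Day 344 to Day 365, and there is no gap.

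Protocol 3.1.3 and SAP 3.2.1 both use 28-day months for the 12 months of follow-up, which favors the first reading. Protocol 4.4 does not say which applies to the trace.

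**The case against.** The best defense is that 9.2.2.4 is titled and built for treatment discontinuation and prohibited therapy, not for loss, so keeping the usual censoring at loss is an ordinary choice. Because the date of loss is undefined, a patient found by the trace might be treated as not lost, and the sentence on observed events would then admit the death. That the deaths would be excluded is therefore a reading of the text, not an established outcome. This stands as far as it goes. But 9.2.2.4 is the plan's only time-to-event analysis of MACE that looks past treatment stop, and a term left open enough to rescue it needs a definition.

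Several stronger readings are tempting, and the documents do not support them:

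- *That data on all withdrawn patients are thrown away.* The records trace is for patients lost to follow-up. Those who stop treatment are telephoned monthly and are not censored for stopping in 9.2.2.4. Those who withdraw all consent can add no new data.
- *That no analysis at all can use a traced death.* The count in 9.2.2.3 states no such censoring.
- *That dating the trace from Visit 1 causes the exclusion.* It can only leave some days unsearched, and it is a separate wording conflict.
- *That the consent limit shares the Visit 1 anchor.* Protocol 14.5 allows follow-up "for a period of not more than 12 months after the patient has entered the trial". Entry is not defined there, and 4.1.1 requires the inclusion criteria to be met before entry, which points to a time after screening.
- *That 0.7 to 3.5 events, up to 25% of the 14, are affected.* That comes from 545 × 0.05 = 27 lost patients × 14/545, times one to five. It gives each lost patient the whole-period risk, when only the time after loss counts, and so roughly doubles the answer.

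One further objection stands and shapes the remedy. Extending a traced survivor to the date last known alive would, for the composite, treat him as free of MI and stroke when only his survival may be known.

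**Conclusion.** The concern holds in a limited form. The protocol requires lost patients to be traced. The SAP's censoring rule, read literally, gives a traced death before Day 336 no route into any time-to-event analysis, including all-cause death, and this conflicts with the stated use of all observed events in 9.2.2.4.

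The expected size is about 0.3 to 1.6 MACEs at 545 patients and 1.4 to 6.4 at the planned 876, with fewer deaths. These figures assume 5% annual drop-out (a planning value, not observed loss), full exposure for the 545, and a hazard after loss of one to five times the rate before it; that multiple has no source in the documents. The matter is not one of power. It deserves correction because one event is 7% of 14 and because the remedy uses data the protocol already requires.

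The Visit 1 date is a separate, smaller inconsistency: at most 21 days untraced with 28-day months, none with calendar months.

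**What to change.** **1. SAP.** Leave the primary analysis as it is.

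- Define loss to follow-up and its date, and say how a patient found by the trace is classified.
- Add a version of all-cause death not censored at treatment discontinuation. Count every death up to Day 336 found by the Protocol 4.4 trace, where consent allows. Censor traced survivors at the date last confirmed alive, at most Day 336.
- In 9.2.2.4, count adjudicated deaths and MACEs found by the trace up to Day 336. Censor traced survivors at the last date to which medical records show them event-free, not at a date of vital status alone.
- In both, censor untraceable patients and those who withdrew all consent at last contact, and report their number by arm.

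**2. Protocol 4.4.** Reconcile the date counted from Visit 1 with the Day 336 end of trial counted from Visit 2, and say which kind of month is meant. As the trial has been terminated, the practical step may be to report how far each trace reached.

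**Cost.** SAP wording, last-known-status dates from data the protocol already asks for, and one additional analysis of death. The remaining weakness is that non-fatal MI and stroke in traced patients are known only where medical records were reached, so 9.2.2.4 will capture deaths more completely than non-fatal events in this group.

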9.3 Secondary Endpoints

If the primary analysis is significant at the two-sided Type I error-level of 5% the testing of the secondary endpoints will proceed as described below.

Key Secondary Analyses

The following analyses are included in the family of key secondary analyses:

Date: 24 Feb 2021 E-Statistical Analysis Plan-19595; Ver.7.0 Supersedes: 6.0 Page 26 of 51

- Time from randomization to the first confirmed (adjudicated) occurrence of CV-related death, non-fatal myocardial infarction or non-fatal stroke
- Time from randomization to confirmed (adjudicated) CV-related death
- Time from randomization to the first confirmed (adjudicated) myocardial infarction

The key secondary endpoints will be controlled for multiplicity (to ensure the family wise error rate is protected at a two-sided 5% Type I error-level) using a fixed-sequence testing method. The order of the testing sequence is as follows:

- 1. Time from randomization to the first confirmed (adjudicated) occurrence of CV-related death, non-fatal myocardial infarction or non-fatal stroke
- 2. Time from randomization to confirmed (adjudicated) CV-related death
- 3. Time from randomization to the first confirmed (adjudicated) myocardial infarction

The remaining secondary endpoints will be analyzed without controlling for multiplicity.

Other Secondary Analyses

- Time from randomization to the first confirmed (adjudicated) stroke
- Time from randomization to first confirmed (adjudicated) unstable angina requiring hospitalization
- Time from randomization to death due to any cause
- Time from randomization to failure in PFS
- Testosterone levels at Days 28, 168 and 336 in the degarelix and leuprolide treatment groups
- Total number of CV-related hospitalizations over the duration of the trial
- Total number of CABG or PCI procedures over the duration of the trial
- Total number of CV-related ER visit events over the duration of the trial
- Changes from baseline in Health-Related Quality of Life (HRQL) as measured by EQ-5D-5L, during the course of treatment period
- The difference in QALY during one year of treatment with degarelix compared to leuprolide
- The change from baseline in the mean DASI and CAQ score during one year of treatment with degarelix compared to leuprolide
- The change from baseline in the mean total and QoL IPSS score during oneyear of treatment with degarelix compared to leuprolide

9.3.1 Time from randomization to the first confirmed (adjudicated) occurrence of cardiovascular-related death, non-fatal myocardial infarction or non-fatal stroke

This endpoint is identical to the primary endpoint, only counting CV-related deaths, and not all cause deaths as failures. The time measured in days, from randomization to first confirmed (adjudicated) occurrence of CV-related death, non-fatal myocardial infarction or non-fatal stroke,

will be analyzed using the Kaplan-Meier estimator of the survival function and the log-rank test of the null hypothesis of equal hazard functions, stratified by age group and region. The p-value of the two-sided log-rank test with significance level of 5% will be presented along with plots of the estimated survival functions for the two treatment groups, stratified by age group and region. The treatment effect of degarelix will be further examined by fitting a stratified Cox regression model. The model will include treatment as a factor, be adjusted for the baseline CV risk factors as appropriate and stratified by age-group and region. The 95% confidence limits and associated p-value for the hazard ratio comparing treatment with degarelix to leuprolide will be presented.

TLF Table: Secondary Endpoint: CV Death + MI + Stroke - FAS

TLF Figure: Secondary Endpoint: CV Death + MI + Stroke - FAS

9.3.2 Time From Randomization to the first (adjudicated) occurrence of the individual components of the MACE composite endpoint

Time from randomization to the first adjudicated occurrence of the individual components of the MACE composite endpoint is defined as the number of days from randomization to the first adjudicated myocardial infarction/stroke. The occurrence of the components of the MACE composite endpoint will be adjudicated by the external independent CEC Committee. In order to correctly assess the treatment effect associated with degarelix with respect to the time to individual components of the MACE composite endpoint, it is necessary to account for the competing risk, death due to other causes. The above components of the MACE composite endpoint will be analyzed separately. The log-rank test stratified by age-group and region will be used to examine the null hypothesis of equal cumulative cause specific hazard functions. The p-value of the two-sided log rank test with significance level of 5% will be presented along with the plots of the estimated cumulative cause specific hazard functions for both treatments obtained from the Nelson-Aalen estimator, stratified by age group and region.

TLF Table: Secondary Endpoint: Time to First Adjudicated Myocardial Infarction - FAS

TLF Figure: Cumulative Cause Specific Hazard Function for Time to First Adjudicated Myocardial Infarction – FAS

TLF Table: Secondary Endpoint: Time to First Adjudicated Stroke - FAS

TLF Figure: Cumulative Cause Specific Hazard Function for Time to First Adjudicated Stroke – FAS

Page 28 of 51

9.3.3 Time from randomization to the first confirmed (adjudicated) unstable angina requiring hospitalization

Time from randomization to the first adjudicated occurrence of unstable angina requiring hospitalization will be analyzed in the same manner as the individual components of the MACE primary endpoint, specified in Section 9.3.2.

TLF Table: Secondary Endpoint: Time to First Adjudicated Unstable Angina Requiring Hospitalization – FAS

TLF Figure: Cumulative Cause Specific Hazard Function for Time to First Adjudicated Unstable Angina Requiring Hospitalization – FAS

